18. RECORDS

Clinical records will be maintained as confidentially as possible by all collaborating institutions. Data will be collected from the collaborating institutions and will be maintained by Clinical Statistics. The investigator will ensure that data collected conform to all established guidelines for coding, collection, key entry and verification. Each patient is assigned a unique patient number to assure patient confidentiality. Any publication or presentation will refer to patients by this number and not by name. The licensed medical records department, affiliated with the institution where the patient receives medical care, maintains all original inpatient and outpatient chart documents. Patient research files are kept in a locked room. They are maintained by the FHCRC data collection staff, which is supervised by an A.R.T. Access is restricted to personnel authorized by the Division of Clinical Research.

19. STATISTICAL CONSIDERATIONS AND TERMINATION OF STUDY

The primary objective of this clinical trial is to evaluate, within the limits of a phase II study, the preliminary efficacy as defined by engraftment, of a regimen consisting of treosulfan and fludarabine followed by allogeneic HCT in patients with nonmalignant inherited disorders. We plan to enroll at least 30 patients on this study. A minimum of 30 patients will be enrolled onto Arm A. The protocol will continue to accrue until this goal is met. There will be no set limit for Arm B: the cord blood arm. Analyses will be carried out separately between Arm A and B. We will be encouraged to continue study of this treatment if at least 27 of 30 patients engraft. Table 5 shows the probability of observing 27 or more successes among 30 patients for several possible true rates of engraftment.

The protocol was modified in January 2011 and September 2011. Due to a higher than anticipated incidence of acute grade III-IV GVHD for both arms in the first 13 patients (5/13 = 38%; 3/8 bone marrow recipients, 2/5 cord blood recipients) the protocol was modified to add rabbit ATG (thymoglobulin) to both arms initially for unrelated recipients (January 2011) and subsequently for the related recipients (September 2011). In addition, due to graft rejection (n=1) and low donor chimerism/inadequate disease response (n=1) in 2 of the 5 patients enrolled onto the cord blood arm, the cord blood arm was modified to increase the TBI from 200 cGy to 300 cGy TBI for non T-cell deficient patients. The revised protocol will reset the target accrual to at least 30 patients as of January 2011, with a minimum enrollment of 30 onto Regimen A (as stated above). The efficacy analysis will be performed separately for the initial 13 patients (Regimen A: n=8, Regimen B: n=5) and those accrued under the modified regimen. Only patients enrolled after this protocol modification will be counted towards the stopping rules.

Table 5. Probability of observing 27 or more successes in 30 patients

| True rate of engraftment | Pr(\geq 27 successes) |
|--------------------------|--------------------------|
| 70% | 0.01 |
| 80% | 0.12 |
| 90% | 0.65 |
| 95% | 0.94 |

The incidence of day 200 transplant-related mortality (TRM) will be monitored in all patients. If there is sufficient evidence suggesting that the true incidence of day 200 TRM exceeds 25% on either arm, enrollment on that arm will be suspended and the DSMB will be convened to make recommendations regarding protocol modification. Sufficient evidence will be an observed rate of day 200 TRM that corresponds to a one-sided 80% confidence interval with a lower limit greater than 25%. These limits will be examined after every 5th enrolled patient becomes eligible for evaluation. In practice, the study arm will be suspended if we observe the following number of TRM in study patients: 3/5, 5/10, 6/15, 8/20, 9/25, 10/30, 12/35, 13/40, 15/45 or 16/50 per disease subgroup per study arm (Regimen A versus Regimen B). Table 6 summarizes the operating characteristics of this stopping rule, for enrollment of up to 50 patients per disease subgroup per study arm (Regimen A versus Regimen B) as estimated from 5,000 Monte Carlo simulations. We will apply stopping rules to regimens A and B separately.

The protocol related to regimen B was modified in April 2012. Stopping rules for excess day 200 TRM were met in October 2011 due to 3 deaths occurring in the 5 patients enrolled since the January 2011 protocol modifications (1 due to multi-system organ failure; 1 due to ARDS/diffuse alveolar damage; and 1 due to gram positive sepsis (strep viridans) with multi-system organ failure, questioned possible sinusoidal obstructive syndrome/veno-occlusive disease). All deaths occurred before day 100, with two very early on post-transplant day 1 and day 7. However, the causes of death did not appear to be related to any single part of the regimen. The Data Safety Monitoring Board met and reviewed the data and recommended the following: The revised protocol will allow up to 5 more patients to be enrolled on regimen B before reconvening the DSMB, with each patient enrolled no sooner than 28 days following the date of transplantation (defined as the date of stem cell infusion) of the previous patient. The stopping rules for this arm (Regimen B) were not reset and will continue as stated in the protocol. The next stopping rule would be triggered at 5/10. Therefore, if 2 of the next 5 patients enrolled dies on Regimen B (cord blood), the stopping rule would be triggered and the DSMB will reconvene.

Table 6. Probability of stopping the trial for excess day 200 TRM

| Number of patients | True rate of event | Probability of stopping |
|--------------------|--------------------|-------------------------|
| 10 | 15% | 0.03 |
| 15 | 15% | 0.04 |
| 20 | 15% | 0.04 |
| 25 | 15% | 0.05 |
| 10 | 35% | 0.32 |
| 15 | 35% | 0.49 |
| 20 | 35% | 0.54 |
| 25 | 35% | 0.63 |
| 10 | 45% | 0.57 |
| 15 | 45% | 0.78 |
| 20 | 45% | 0.84 |
| 25 | 45% | 0.91 |

The incidence of graft rejection will also be monitored in all patients. Regimen A and B will be monitored/analyzed separately. If there is sufficient evidence to suggest that the true incidence of graft rejection exceeds within the first 365 days 10% on either arm, enrollment will be suspended on that arm and the DSMB will be convened to make recommendations regarding protocol modification and/or dose escalation. Sufficient evidence will be an observed rate of graft rejection that corresponds to a one-sided 80% confidence interval with a lower limit greater than 10%. These limits will be examined after every 5th enrolled patient becomes eligible for evaluation. In practice, the study arm will be suspended if we observe the following number of graft rejections in study patients: 2/5, 3/10, 3/15, 4/20, 5/25, 5/30, 6/35, 7/40, 7/45 or 8/50 per disease subgroup per study arm (Regimen A versus Regimen B). Table 7 summarizes the operating characteristics of this stopping rule for enrollment of up to 50 patients per disease subgroup, as estimated from 5,000 Monte Carlo simulations.

Table 7. Probability of stopping the trial for excess graft rejection

| Number of patients | True rate of event | Probability of stopping |
|--------------------|--------------------|-------------------------|
| 10 | 5% | 0.03 |
| 15 | 5% | 0.05 |
| 20 | 5% | 0.05 |
| 25 | 5% | 0.05 |
| 10 | 20% | 0.38 |
| 15 | 20% | 0.62 |
| 20 | 20% | 0.68 |
| 25 | 20% | 0.72 |
| 10 | 30% | 0.67 |
| 15 | 30% | 0.88 |
| 20 | 30% | 0.93 |
| 25 | 30% | 0.95 |

Therefore, **stopping rules** will be imposed for:

Day 200 TRM > 25% (3/5, 5/10, 6/15, 8/20, 9/25, 10/30, 12/35, 13/40, 15/45, 16/50) per disease subgroup per study arm (Regimen A versus Regimen B).

Day 365 Graft rejection (defined as CD3 T cell chimerism < 5%) > 10% (2/5, 3/10, 3/15, 4/20, 5/25, 5/30, 6/35, 7/40, 7/45, 8/50) per disease subgroup per study arm (Regimen A versus Regimen B)

Day 100 Grade III/IV GVHD >15% for Arm A +rATG PBSC grafts 2/5, 3/10, 4/15, 5/20, 6/25, 7/30, 8/35, 9/40, 10/45, or 11/50

The dosing of treosulfan on protocol 2256 was modified in June 2013, specifically the dose of Treosulfan was decreased for smaller children. However, three of the first five patients treated with the reduced dose have experienced poor engraftment. Therefore the original dose of treosulfan was reinstated in April 2014. The protocol accrual will continue to a total of 60 patients in Arm A with Treosulfan/Fludarabine/rATG, so as to ensure adequate numbers of smaller children will be treated at the original dose, since among the original 30 patients only a small number were <0.5 m² body surface area. As stated above, the initial 8 patients transplanted on Regimen A with Treosulfan and fludarabine only do not count towards the accrual goal of 60. Therefore the total number of patients accrued on Regimen A will be 68. The same stopping rules for TRM and rejection applied to the first 30 patients in Arm A will be applied separately to the additional 30 patients in Arm A; however, accrual to Arm B will continue as before under the same stopping rules.

In October/November 2015 Regimen A of the protocol was modified to increase accrual to a minimum of 20 patients for each subgroup of patients (for example, primary immunodeficiency diseases, hemophagocytic disorders, hemoglobinopathies, and marrow failure disorders) who receive Treosulfan, fludarabine, and rabbit ATG. The protocol will continue to accrue until a minimum of 20 patients are in each subgroup, in order to better evaluate the safety and effectiveness of the regimen in each subgroup. There is no limit to the overall accrual to Regimen A as long as the minimum of 20 patients per subgroup has not been reached and each subgroup will continue to accrue until all subgroups reach a minimum of 20 patients. We estimate the overall accrual will be 100-120 patients. Stopping rules for TRM and graft rejection will be applied separately in each disease subgroup of patients who receive Treosulfan, fludarabine, and rabbit ATG conditioning. There are additional patients with nonmalignant diseases that do not fit into one group that have enrolled onto the protocol and will continue to enroll onto the protocol such as metabolic disorders, autoimmune disorders, or other rare nonmalignant diseases. We will continue to enroll these patients but they will not count towards the stopping rules or enrollment since we do not anticipate very many of these patients. However, they will be reviewed by the data safety monitoring board. Accrual to Arm B will continue as before under the same stopping rules.

In March 2017, the protocol was modified to allow the use of both bone marrow and cord blood from the same HLA-matched sibling donor. Specifically, at the discretion of the PI, bone marrow and cord blood cells from the same HLA-matched sibling donor may be used together for transplantation in cases where such cord blood cells were previously stored. The patients enrolled onto the protocol who receive both bone marrow and cord blood from the same HLA-matched sibling donor will be enrolled onto Regimen A of the protocol and analyzed with this group.

In March 2018, the protocol was modified to prioritize PBSC (Regimen A) as the preferred stem cell source when feasible. This change was made with the goal of improving donor chimerism. PBSC has a higher risk of graft versus host disease; therefore, a stopping rule for grade III-IV GVHD will be added to the protocol – Regimen A only. Since bone marrow will still be allowed on Regimen A, we will apply this stopping rule to PBSC transplants. If there is sufficient evidence to suggest that the true incidence of grade III-IV GVHD at day 100 exceeds 15% (Regimen A), enrollment will be suspended on that arm and the DSMB will be convened to make recommendations regarding protocol modification. The stopping rule would be triggered if 2 of 5, 3 of 10, 4 of 15, 5 of 20, 6 of 25, 7 of 30, 8 of 35, 9 of 40, 10 of 45, or 11 of 50 experience grade III-IV GVHD. This stopping rule will not be by disease subgroup but for all PBSC transplants. The current PBSC transplants on the protocol will be included in this stopping rule.

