Several studies have demonstrated efficacy of conventional marrow transplantation using HLA-identical sibling donors¹⁷⁻²⁵ and unrelated donors²⁶⁻²⁸ for cure of thalassemia and other hemoglobinopathies. Stable mixed chimerism has been documented in a number of patients after conventional regimens and has been associated with cure of disease.^{20,29} Mortality resulted from infection, pneumonitis, graft rejection, and GVHD. Again, pre-transplant patient characteristics were the most important factors that predicted outcome after HCT. Patients with liver fibrosis or hepatomegaly had a 2-fold increase in risk of mortality. Older age was also associated with worse outcome. Recently, Iannone et al. published results on 7 patients with sickle cell disease (n=6) or thalassemia (n=1) who received bone marrow or peripheral blood stem cell grafts from HLA-identical siblings following conditioning with 200 cGy TBI and fludarabine [30 mg/m² x 3 days (n=2) or 5 days (n=5)] alone or combined with ATG (n=2).³⁰ Although this regimen resulted in minimal toxicity, 6 of the 7 patients lost their grafts following tapering of the immunosuppression. These results suggest that donor engraftment is more difficult to achieve among patients with hemoglobinopathies than what has been found in patients with malignancies. One possible explanation for this is that patients with hemoglobinopathies may have been more sensitized to donor minor histocompatibility antigens by blood transfusions. Therefore, in order to improve the engraftment rate among high-risk patients with thalassemia and sickle cell disease, a more aggressive conditioning regimen may be required in order to overcome these barriers.

4) Osteopetrosis.

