More recently, Sauer⁶³ et al. published on 3 patients with Shwachman-Diamond Syndrome who received treosulfan (12 g/m²/d x 3), fludarabine (30 mg/m²/d x 6), and Melphalan (140 mg/m²/d x 1) in combination with CAMPATH-1H (0.1 mg/kg x 2) in 2 cases and ATG in one case followed by HLA-identical sibling (n=1), HLA-matched unrelated donor (n=1) or 9/10 matched unrelated cord blood graft. All patients engrafted at 24, 31, and 26 days after HCT and had 100% donor chimerism at last follow up. Two of the 3 patients are alive at 9 and 20 months after HCT. The third patient who received a cord blood graft died 3 months after HCT of IPS. Greystoke and colleagues recently published a retrospective analysis of 32 pediatric patients undergoing HCT for nonmalignant diseases including primary immunodeficiency (n=18), metabolic disorders (n=9), osteopetrosis (n=4) and thalassemia (n=1).⁶⁴ Patients received a total treosulfan dose of 36 g/m² (n=6) or 42 g/m² (n=26) given in three divided doses on consecutive days. A variety of other conditioning agents were used depending on the stem cell source and donor type including fludarabine (150 mg/m²) Cyclophosphamide (200 mg/m²), plus or minus Campath or ATG. HLA-matched or mismatched related or unrelated bone marrow (n=17), peripheral blood (n=9), and cord blood (n=5) grafts were used as the stem cell source. Post HCT immunosuppression included Cyclosporine alone or combined with Mycophenolate Mofetil, methylprednisolone, or methotrexate. Twenty eight patients (87.5%) established donor cell engraftment; however, 4 patients have required additional transplantation procedures to maintain adequate donor derived hematopoiesis. With a median follow up of 471 days, 27 (84%) of the patients survive. One patient died early (day +4) due to sinusoidal obstructive syndrome and four other deaths were late due to disease progression, GVHD or infection. The incidence of GVHD was very low with 6 (19%) patients developing acute grade II (n=4) or grade III (n=2) acute GVHD and 4 (13%) patients developing chronic GVHD. Although multiple different donors and conditioning regimens were used, these results are encouraging in pediatric patients with nonmalignant disorders.

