Bernardo et al recently published on 20 patients with Thalassemia who were conditioned with Thiotepa (8 mg/kg; day -7), Treosulfan (14 g/m²; days -6 to -4), and fludarabine (40 mg/m²; days -6 to -3) followed by HLA matched related (n=3) or unrelated (n=17) bone marrow grafts. GVHD prophylaxis consisted of Cyclosporine and methotrexate. Pretransplantation ATG (10 mg/kg; days -5 to -3) was administered to all the unrelated graft recipients. Two patients experienced secondary graft failure. Cumulative incidence of TRM was 5% and the 2 year probability of survival and thalassemia-free survival was 95% and 85%, respectively.

2c. Phase I/II Study of Treosulfan and fludarabine in the United States- Protocol 1931 -Preliminary Results

Forty-six patients, median age 41 years (5-59 years), with acute myeloid leukemia in first remission (n=22), second remission (n=9), partial remission or relapse (n=5) or ALL in second remission (n=2) or myelodysplastic syndrome (n=8) have been enrolled on study. Eight of the AML patients had secondary (treatment-induced) AML and 5 patients had failed a previous transplant. Most patients had underlying conditions that made them poor candidates for conventional myeloablative regimens. All patients received therapy as per protocol with treosulfan (5 at dose level 1 or 12 g/m²/day, and 41 at dose level 2 or 14 g/m²/day) on days -6 to -4 and fludarabine (30 mg/m²/day) on days -6 to -2. Patients received HLA-matched sibling grafts (n=1 marrow, n=23 PBSC), or unrelated grafts (n=6 marrow, n=16 PBSC) on day 0. Neutrophil engraftment occurred in 100% of 43 evaluable patients at a median of 17 (range, 5-30) days after HCT. Acute graft-versus-host disease

(GVHD) has been observed in 25 of 43 evaluable patients (grade I-II). Chronic GVHD has been observed in 13 of 35 evaluable patients. Dose limiting toxicity has been observed in 1 of 46 patients (**Table 1**). There have been 9 reportable serious adverse events, 2 of which were deemed study drug related. One patient died of systemic aspergillosis on day 10. Ten patients have relapsed at a median of 76 (26-184) days, of which 7 have died of disease recurrence. Thirty-six patients are alive and disease-free, with a median follow-up of 204 (range, 10-711) days after HCT.

| Table 1: Outcomes Summary | | | |
|----------------------------------|----------------|----------------|---------------|
| Probability (%) | 100-day | 200-day | 1-year |
| OS | 93 | 81 | 76 |
| EFS | 81 | 75 | 72 |

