4. OBJECTIVES

A. Primary Objectives:

The primary objective of this clinical trial is to evaluate, within the limits of a phase II study, the preliminary efficacy as defined by engraftment, of a regimen consisting of treosulfan and fludarabine followed by allogeneic HCT in patients with nonmalignant inherited disorders.

B. Secondary Objectives:

1. Incidence of non-relapse mortality 200 days and 1 year post-HCT
2. Incidence of grade II-IV acute GVHD
3. Incidence of chronic GVHD – as defined as those patients requiring systemic immunosuppression
4. Donor chimerism on days +28 and +100
5. Assess disease response following HCT
6. Immune reconstitution following HCT
7. Incidence of infections
8. Overall survival

C. Exploratory Objectives:

1. Pharmacokinetic parameters of treosulfan and treosulfan monoepoxide

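### Must the protocol define engraftment before the 27-of-30 criterion can be used?

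*Combined protocol and SAP*

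**What the plan says.** Section 4A sets the primary objective as "the preliminary efficacy as defined by engraftment, of a regimen consisting of treosulfan and fludarabine", followed by allogeneic transplantation. Section 19 turns this into a count: "We will be encouraged to continue study of this treatment if at least 27 of 30 patients engraft". Table 5 gives the chance of reaching 27 or more at true rates of 70%, 80%, 90% and 95%. Regimens A and B are analysed separately, and Regimen B has no set accrual.

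Four other places touch on engraftment, each for its own purpose:
- Section 19 defines graft rejection as CD3 chimerism under 5%, to day 365, for a stopping rule with a 10% limit.
- Section 4B lists donor chimerism at days +28 and +100 as a secondary objective, with no cut-off.
- Section 3F names CD33 myeloid engraftment as the aim of preferring PBSC.
- Section 14B uses an ANC above 500/µL for 3 days to set how often blood counts are drawn.

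None of these is linked to the 27-of-30 count.

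**The concern.** A primary endpoint that is a bare count needs a rule for what is counted, and the background sections use several. Section 3C.2c reports "Neutrophil engraftment occurred in 100% of 43 evaluable patients". Section 3C.2b separates establishing a graft from keeping it: "Twenty eight patients (87.5%) established donor cell engraftment; however, 4 patients have required additional transplantation procedures to maintain adequate donor derived hematopoiesis". Section 3A.2 distinguishes full from mixed chimerism.

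The trial has also produced patients who are hard to classify. Section 19 mentions changes "due to graft rejection (n=1) and low donor chimerism/inadequate disease response (n=1) in 2 of the 5 patients" on the cord blood arm, notes that "three of the first five patients treated with the reduced dose have experienced poor engraftment", and says of three Regimen B deaths: "All deaths occurred before day 100, with two very early on post-transplant day 1 and day 7".

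With an allowance of three failures, the same 30 patients could pass under one reading and fail under another. Section 19 already speaks of an original 30, so the reading might be chosen with the results in view.

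**Working it through.** **1. The plan's own figures.** Inputs from Section 19: n = 30, pass mark 27. P(pass) = Σ C(30,x) pˣ(1−p)³⁰⁻ˣ for x = 27 to 30.

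| True rate | Table 5 | Recomputed |
|---|---|---|
| 70% | 0.01 | 0.009 |
| 80% | 0.12 | 0.123 |
| 90% | 0.65 | 0.647 |
| 95% | 0.94 | 0.939 |

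The table is right.

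**2. How far a definition could move the result.** Let k of the 30 be disputed and the other 30 − k engraft at rate p (assumed). If the disputed patients count as engrafted, P = Pr[Bin(30−k, p) ≥ 27−k]. If they count as failures, P = Pr[Bin(30−k, p) ≥ 27].

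| k | p = 0.90: engrafted / failed | p = 0.95: engrafted / failed |
|---|---|---|
| 1 | 0.67 / 0.44 | 0.95 / 0.83 |
| 2 | 0.70 / 0.22 | 0.95 / 0.59 |
| 3 | 0.72 / 0.06 | 0.96 / 0.25 |

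For k = 3 as failures the formula is p²⁷; for example 0.95²⁷ = 0.25. Leaving patients out instead needs a pass mark that the protocol does not give. With two left out and p = 0.95, requiring 26 of 28 gives 0.84 and requiring 25 of 28 gives 0.95.

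**3. The cited series.** In Section 3C.2b, 28/32 = 0.875 gives P = 0.47. If all four further transplants were among the 28, sustained engraftment is 24/32 = 0.75 and P = 0.04. If they were the four who did not engraft (32 − 28 = 4), the rate stays at 28/32 and the contrast disappears. The wording favours the first reading but does not settle it, so the range is 0.04 to 0.47.

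In Section 3C.2c, 43/43 gives 1.00. Counting the three non-evaluable patients as failures gives 43/46 = 0.935 and P = 0.87. Those are leukemia and MDS patients of median age 41, with follow-up starting at 10 days, so the three may only have been too early to assess.

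**4. Whether the trial's own cases lie in the 30.**
- The rejection and low-chimerism cases are cord blood recipients among the initial 13 patients, whose efficacy analysis is separate. Those five are 4/5 engrafted if only rejection fails and 3/5 if low chimerism also fails, but neither figure enters the Regimen A count.
- The day 1 and day 7 deaths are Regimen B.
- The three patients with poor engraftment received the reduced dose introduced in June 2013. Their arm is not stated, nor whether they belong to the original 30.

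No described case can be placed in the Regimen A 30, and no engraftment count for them is given.

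**5. What depends on the count.** Section 19 attaches encouragement to it, with no null rate, significance level or target power. Accrual was extended to 60 because few smaller children were among the original 30, and later to at least 20 per disease subgroup (estimated 100–120 overall). Neither step cites 27 of 30. Suspension is governed by the TRM, rejection and PBSC GVHD rules, which have their own definitions and boundaries.

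**6. What a written definition would add.** One could be assembled from figures in the protocol: ANC above 500/µL for 3 days by day +42 (the upper end of expected aplasia in Appendix I), donor CD3 never under 5% to day 365, and no further stem-cell infusion. It would pass a patient with 6% donor CD3 whatever the CD33, although Section 3F says many of these diseases need high donor levels in several lineages. It would fail a fully donor patient who received a cell boost.

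Carrying a further graft into the rejection stopping rule would also change that rule. Crossing 2/5, 3/10, 3/15 or 4/20 has probability 0.052 at a 5% event rate, 0.079 at 6% and 0.111 at 7%. For at least one of four independent subgroups, 1 − (1 − P)⁴ is 0.19, 0.28 and 0.38.

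**The case for a change.** The best case for a change is that engraftment is the only primary efficacy endpoint and the spreads in step 2 are as wide as moving between rows of Table 5. Regimen A is not exempt: Section 3F says mixed chimerism remains a challenge with this regimen, and the response to the reduced-dose cases was to extend Arm A. Reading engraftment as absence of rejection is natural, since 27/30 = 90% is the complement of the 10% rejection limit. It is nowhere stated, however, and it leaves early death and a further graft open. Late loss is a genuine possibility. Section 3A.3 reports that "6 of the 7 patients lost their grafts following tapering of the immunosuppression", although that series used 200 cGy TBI and fludarabine without treosulfan.

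Most of this stands as a description of the gap. It does not show that the gap changed a result or that a particular definition is the right one. The worry about choosing with results in view is fair, but writing the rule now does not cure it. The original 30 are mentioned in connection with the return to the original dose in April 2014, while the current text describes a March 2018 change and has a reference list dated November 2019. For those patients any new rule is also after the fact. Showing the count under each reasonable reading protects the reader better than fixing one reading late.

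**Conclusion.** The definition is missing, and no change to the plan follows. This is an unwritten detail rather than a stated rule that gives a wrong answer, and analysts can fill it sensibly. They can say which definition and which 30 Regimen A patients were used, relate it to the day-365 rejection definition, and give the count with early deaths and further grafts scored both ways. Most of the data needed are already in the recommended schedule: daily blood counts to neutrophil recovery, and lineage-specific chimerism from day +28 onward. Low donor chimerism is reported in any case as a secondary objective. Because the post-transplant tests are recommended rather than required, some values may be missing, and the report should say how many.

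The possible effect is large under assumption (0.96 against 0.25 with three disputed patients and 95% in the rest) but not demonstrated, since no described case can be placed in the 30 and no count is given. The conclusion rests on two readings of Section 19: that no accrual or suspension decision now depends on 27 of 30, and that the original 30 were treated before the current text. The point would become material if the reported count fell within a few patients of 27 and only one definition were shown.

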17. DATA AND SAFETY MONITORING PLAN AND ADVERSE EVENT REPORTING

17A. Monitoring the Progress of Trials and the Safety of Participants

The principal investigators (PI) monitor multi-institutional clinical trials, with oversight by the Medical Monitor, a Data Safety and Monitoring Board (DSMB), the Data and Safety Monitoring Committee (DSMC) and the Institutional Review Board (IRB). The PI reviews outcome data for each individual patient on an ongoing basis.

This multi-center protocol has a DSMB responsible for monitoring patient safety by reviewing protocol data and safety endpoints. The DSMB meets twice a year and all outcome data is reviewed including all adverse events reported to the coordinating center (FHCRC) along with those officially reported to the FHCRC IRO. The DSMB confirms that the trial has not met any stopping rules and reviews any patient safety problems necessitating discontinuation of the trial. A report from the DSMB is submitted to the FHCRC IRB, the IND sponsor, the DSMC Chairman, Protocol Office, and the trial coordinators/local PIs of this protocol. The DSMB will discontinue the review of outcomes when this protocol is closed to accrual. Furthermore, the FHCRC also has a DSMC that reviews the progress of the protocol with respect to the monitoring plan at the time of each annual renewal. As with initial review, annual IRB review and approval is also required.

Flow of information concerning clinical trial participants originates with the clinicians and nurses in the clinic or referring clinicians at other institutions and is transmitted to the FHCRC Trial Coordinator. At the FHCRC, health care providers and rotating attending physicians assess patients and record their observations regarding toxicity and response outcomes in the medical record. Thus, multiple health care providers provide independent observations and participate in monitoring this trial. The PI may be a clinician for some patients entered on this trial. However, assessments are the sum total of the primary health care provider (fellow or physician assistant), floor or outpatient nurse and the PI or other attending clinician involved with the patient avert a possible conflict of interest having the PI as the attending clinician for protocol patients. If determination of adverse events is controversial, co-investigators will convene on an ad hoc basis as necessary to review the primary data and render a decision.

17B. Adverse Event Definitions

a. Adverse Event

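### Does the undefined evaluability term in the day-200 TRM and day-365 rejection stopping rules let enrolment run on after a limit is already crossed?

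*Combined protocol and SAP*

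**What the plan says.** Section 19 sets limits at every fifth patient, applied per disease subgroup and regimen. The TRM limits run from 3/5 to 16/50 and the rejection limits from 2/5 to 8/50. The rejection rule concerns a true incidence that "exceeds within the first 365 days 10% on either arm". Both rules carry the sentence "These limits will be examined after every 5th enrolled patient becomes eligible for evaluation", and no section defines the term.

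Other text in Section 19 bears on how the rules operate:

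- Each rule then goes straight to counts. For TRM: "In practice, the study arm will be suspended if we observe the following number of TRM in study patients".
- After the Regimen B suspension, the next trigger is put as "if 2 of the next 5 patients enrolled dies on Regimen B (cord blood), the stopping rule would be triggered".
- The past trigger is recorded this way: the TRM rules "were met in October 2011 due to 3 deaths occurring in the 5 patients enrolled since the January 2011 protocol modifications".
- The later grade III-IV GVHD rule has no timing sentence: "The stopping rule would be triggered if 2 of 5, 3 of 10, 4 of 15, 5 of 20".

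Section 17A adds continuous patient-level review by the principal investigator, and "The DSMB meets twice a year and all outcome data is reviewed". At those meetings the DSMB confirms that no stopping rule has been met.

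**The concern.** A patient could count as evaluable at transplant, at the event, or after the full 200 or 365 days. For endpoints named by day 200 and day 365, the third meaning is a fair literal reading. Patients still in follow-up can only add events, so once 2 of 5 have rejected, more follow-up cannot undo the crossing. A look that waited would learn nothing that could change its result, while further patients were conditioned and transplanted on an arm that had already failed its limit. Two people applying the same text could suspend a subgroup months apart. The exposure would be largest for rejection, where the window is a full year.

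**Working it through.** **1. The limits reproduce.** Each limit is the smallest r with P(X ≥ r | n, p0) < 0.20, which is the same as an exact one-sided 80% lower limit above p0.

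- TRM, p0 = 0.25, n = 5: P(X ≥ 2) = 0.367 and P(X ≥ 3) = 0.104, so 3/5.
- Rejection, p0 = 0.10, n = 5: P(X ≥ 1) = 0.410 and P(X ≥ 2) = 0.081, so 2/5.

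All 20 stated limits match.

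**2. Tables 6 and 7 reproduce without calendar time.** An exact recursion with looks every five patients and complete outcomes gives, at n = 10, 15, 20, 25:

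| Rule, true rate | Recursion | Plan |
|---|---|---|
| TRM 35% | 0.33, 0.50, 0.55, 0.64 | 0.32, 0.49, 0.54, 0.63 |
| Rejection 20% | 0.39, 0.62, 0.69, 0.73 | 0.38, 0.62, 0.68, 0.72 |

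All 24 entries agree within 0.02. A count reached early among the first n is still reached when those n are complete. Counting as events occur and waiting therefore give identical stopping probabilities, and only the date differs.

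**3. Size of the lag if looks wait.** For a limit of c events in n patients enrolled at times t_i, with window W:

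- Count-based stop = max(time of the c-th event, t_n).
- Waiting stop = the time when each of the first n has had an event or reached t_i + W.
- Lag = the difference. It cannot exceed W, because the waiting stop is at most t_n + W and the count-based stop is at least t_n.

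The documents give neither subgroup accrual nor event timing, so both are assumed: Poisson accrual, looks at n = 5 to 20, true TRM 35-45%, true rejection 20-30%.

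| Rule | Patients per subgroup-year | Early events*: median lag, mean further patients | Whole window: median lag, mean further patients |
|---|---|---|---|
| TRM | 2-3.4 | 83-95 days, 0.5-0.9 | 77-89 days, 0.5-0.9 |
| TRM | 6 | 95-98 days, 1.6-1.7 | 78-83 days, 1.4 |
| TRM | 10 | 100-101 days, 2.7-2.8 | 75-78 days, 2.2-2.3 |
| Rejection | 2-3.4 | 297-335 days, 1.3-2.5 | 244-282 days, 1.2-2.1 |
| Rejection | 6 | 284-292 days, 4.4-4.5 | 208-217 days, 3.4 |
| Rejection | 10 | 275-276 days, 7.4 | 183-191 days, 5.1-5.3 |

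*TRM on days 1-150, rejection on days 14-200. Repeat runs move the medians by up to about 10 days.

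At 30.44 days per month, the rejection medians run from 183/30.44 = 6.0 to 335/30.44 = 11.0 months, and the TRM medians from 75/30.44 = 2.5 to 101/30.44 = 3.3 months. Individual lags run from near 0 up to the window length.

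The only accrual rates the documents imply are for two earlier groups: five Regimen B patients in at most 303 days (5 × 365/303 = 6.0 per year or more) and five reduced-dose patients in at most 333 days (5 × 365/333 = 5.5 per year or more). Neither is a present disease subgroup.

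**4. Which reading the text supports.**

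- The suspension sentences speak of observed numbers. The closing list in Section 19 gives counts only.
- The Regimen B trigger is two deaths among the next five enrolled, with no follow-up condition.
- October 2011 fits both readings. A completed day-200 look that month needs the fifth transplant by some date between 15 March and 14 April 2011, which is possible.
- In the dose episode, "three of the first five patients treated with the reduced dose have experienced poor engraftment" led to reversal between June 2013 and April 2014. That is at most 333 days, so none of the five could have reached day 365. It was not a formal crossing, but it shows the team acting on events as they appeared.

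The sentences also fit together. The timing sentence can say when a block is complete enough to be cleared, and the count sentence says when the arm is suspended.

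**5. The backstop.** Twice-yearly meetings are about 183 days apart, so a DSMB using running counts acts within 183 days of a crossing (median 91). At 2-3.4 patients per year, net of that review, the TRM lag has median 0 days and a mean of 0.2-0.4 further patients. For rejection, the mean number of further patients falls to about 0.9-1.7 (2.2-3.1 at 6 per year).

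**The case for a change.** The strongest case for a change is that leaning is not defining. The phrases about observed counts give numbers without saying whether a look waits. The timing sentence is the only one about timing, and the GVHD rule shows that the rules are not worded alike. The DSMB must confirm that no rule has been met, which presupposes knowing when one is met. The 24-hour notice in Table 4 covers fatal or life-threatening events, so a non-fatal rejection might not prompt it. At 2-3.4 patients per year, the waiting lag for rejection exceeds the 183-day DSMB interval in 68-76% of crossings (63-65% if events spread over the year). One added sentence would cost almost nothing.

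What stands is that the term is undefined and that the conditional arithmetic is right. What does not stand is the inference to harm. Every figure needs the less natural reading, an assumed accrual rate and assumed event timing, and no instance of waiting is on record. For Regimen B after April 2012, the DSMB had to reconvene after at most five more patients regardless of follow-up. The principal investigator, IRB, IND sponsor or DSMC may suspend the trial (Section 17I).

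A related worry is that Section 17A ends DSMB outcome review when accrual closes, before the last patients reach day 200 or 365. By then no enrolment rule is left to act on, and follow-up forms continue under Section 17J.

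**Conclusion.** No change to the plan is needed. The term is undefined, but the neighbouring sentences suspend on observed counts, and a trial team would apply them that way. The limits and Tables 6 and 7 hold either way. For TRM, the hypothetical lag (medians 75-101 days) is about the typical wait for the next DSMB meeting. For rejection, a median lag of roughly 6 to 11 months would arise only if every party waited for full follow-up. That range rests on assumed accrual of 2 to 10 patients per subgroup-year and on assumed rejection timing, and it is before allowing for DSMB review. Recording the count-based reading would do no harm, but no limit, table or analysis depends on it. The conclusion would change if there were evidence that looks had in fact been held until day 365 with the count already reached.
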